### 6.2. Primary Endpoint: Study Hypothesis

The primary endpoint of the study is a composite safety and effectiveness measure defined as device and/or procedure-related death or MI through 30 days or any TLR, target limb(s) major amputation, or restenosis through 9 months post-index procedure.

The BOLSTER study is a single-arm study of treated subjects receiving the LIFESTREAM™ Covered Stent compared to a PG derived from published literature of stents for the treatment of iliac artery stenosis/occlusion. Specifically, the PG rate was derived as 19.5%.

The primary endpoint will be evaluated by the following hypothesis:

H0: The proportion of subjects in the LIFESTREAM™ Covered Stent group (PBBX) with events in the primary endpoint is greater than or equal to that of the PG of 19.5%.

H1: The proportion of subjects in the LIFESTREAM™ Covered Stent group (PBBX) with events in the primary endpoint is less than that of the PG of 19.5%.

$$\mathbf{H_0: P_{BBX} \geq 19.5\% \quad \text{vs.} \quad H_1: P_{BBX} < 19.5\%}$$

A one-sided p-value will be derived based on an exact binomial test. The study device will be considered to have achieved the primary objective if the one-sided p-value is less than 0.0335 at interim analysis or 0.0325 at final analysis (see section 6.8).

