## 6.6. Handling of Missing Data

Study endpoints may be missing due to withdrawal of consent, investigator's decision, lost to follow-up and death. As long as the missing data is unrelated to the study intervention and the observed and unobserved data, limiting the analysis to those subjects who contribute endpoints produces unbiased estimates of the event rates.

Additionally, Kaplan-Meier survival analyses will be performed to estimate the event rates at various time-points. In survival analyses, unobserved endpoints are a standard part of the analysis. They are known as censored observations.

The reason for missing data for all subjects will be reported. If there is any indication that missing data is related to the study intervention, a worst-case analysis may be performed in addition to the standard analysis. In a worst-case analysis, a failure of effectiveness or safety will be assumed to have occurred at the time the subject was censored.

In addition, regardless of whether missing data are related to the study intervention, a tipping-point analysis will be performed, in which assumptions about missing data are varied from worst-case to best-case to examine at what point the missing data would alter the results of the analysis.

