### 6.8. Interim Analysis

An interim analysis will be performed when all of the first 103 enrolled subjects (at two thirds of the originally planned sample size) either complete the 9-month visits or discontinued from the study. The primary analysis at interim will be based on the first 103 enrolled subjects and no others whether or not there are additional subjects who may have completed their 9-month visits or discontinued at the time.

The linear alpha spending function will be used to control for the overall study-wise type I error rate of 0.05 (Proschan et al, 2006, Chapter 5 and 14). The null hypothesis will be rejected at interim based on  $n=103$  (93 evaluable) if the one-sided p-value is less than 0.0335 (calculated by R package ldbounds). If unsuccessful at interim, the null hypothesis will be rejected based on  $n=154$  (139 evaluable) if the one-sided p-value is less than 0.0325 (calculated by R package ldbounds).

A simulation study (Table 2) was performed to evaluate the operating characteristics of the procedure described above. Based on 100,000 simulations, the probability of achieving success at the interim analysis, the overall power of study (i.e., the probability of achieving success either at interim or at final analysis), and the probability of achieving success at interim but failing the final analysis were estimated with various assumptions of the composite event rate, including under the null hypothesis. Additionally, study power without an interim analysis was estimated as well for each of the scenarios.

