**Table 2: Simulation results**

True Event Rate	Interim Analysis (IA) success	Overall study power with IA	Reject at IA but fail at Final	Study power without IA
19.5%	1.8%	3.8%	0.8%	4.9%
12.5%	37.9%	64.7%	2.1%	71.7%
11.5%	49.1%	77.0%	1.6%	82.8%

10.5%	61.3%	87.1%	1.0%	91.1%
9.5%	73.3%	93.7%	0.5%	95.9%
8.5%	83.5%	97.5%	0.2%	98.6%
7.5%	91.1%	99.3%	0.1%	99.6%
6.5%	96.0%	99.9%	<0.1%	99.9%

When data were simulated under the null hypothesis, i.e., the composite event rate is 19.5%, there is a risk of 1.8% that the null hypothesis will be rejected falsely at interim and an overall false positive risk of 3.8%, which is below the study-wise type I error rate of 0.05.

When data were simulated under the alternative hypothesis, e.g., if the true composite event rate is 10.5% as originally assumed in the sample size calculation, there is a 61.3% chance the study will meet its primary objective at interim with two thirds of the planned sample size and a risk of 1.0% of failing the final analysis after declaring success at interim. By adding the interim analysis, the overall power of the study decreases slightly to 87.1% from the original designed 90% power. However, if the true composite event rate is a few percentage points better than originally assumed, for example at 8.5%, there is a 83.5% chance the study will declare success at interim and the overall power of the study is 97.5% with very little risk of achieving success at interim but failing at final analysis.

The simulation results show that the proposed interim analysis can potentially achieve study success faster with two thirds of the planned sample size, particularly if the true composite event rate is lower than originally assumed. It is unlikely that a final analysis would fail after success is achieved at interim. The added interim analysis may cause some loss of overall study power, but the amount of loss is small.

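### Does the fixed final cut-off of 0.0325 give away power that the 5% type I error limit would allow?

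*Combined protocol and SAP*

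**What the plan says.** Section 6.8 states the aim: "The linear alpha spending function will be used to control for the overall study-wise type I error rate of 0.05". It attaches the interim cut-off to 103 subjects with 93 evaluable, and gives the final cut-off, for 154 subjects, as "139 evaluable) if the one-sided p-value is less than 0.0325 (calculated by R package ldbounds". Section 6.2 repeats both as plain numbers: success requires that "the one-sided p-value is less than 0.0335 at interim analysis or 0.0325 at final analysis". Neither section gives a rule for recalculating the final cut-off if the evaluable numbers differ.

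Table 2 in Section 6.8 reports a simulated overall false positive risk of 3.8% at the 19.5% performance goal. At the assumed 10.5% event rate, the text under the table says that "the overall power of the study decreases slightly to 87.1% from the original designed 90% power", and it concludes: "The added interim analysis may cause some loss of overall study power, but the amount of loss is small".

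The evaluable numbers can vary. Section 5.5 does not replace withdrawn subjects. Section 6.6 relies on complete cases under a stated condition: "As long as the missing data is unrelated to the study intervention and the observed and unobserved data", it says, "limiting the analysis to those subjects who contribute endpoints produces unbiased estimates of the event rates". It also commits to a sensitivity check: "a tipping-point analysis will be performed, in which assumptions about missing data are varied from worst-case to best-case".

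**The concern.** The 0.0325 final level is what linear spending gives if about 3.35% has been used at the interim look. An exact binomial test cannot use exactly 3.35%. At 93 evaluable it stops at 10 events or fewer and uses 1.78%. The unused part is not returned to the final test, and the final test is discrete too, so some of the 5% can go unused.

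Since the evaluable numbers are unlikely to be exactly 93 and 139, the final limit may sometimes be one event tighter than a 5% overall error would permit. A trial landing on that one event count would fail where an equally valid rule would have passed it. Table 2's power would also overstate the power averaged over plausible counts.

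**Working it through.** **Inputs.** Null rate 19.5% and assumed rate 10.5% (Section 6.7); exact one-sided binomial test (Section 6.2); cut-offs 0.0335 and 0.0325 with 93 and 139 evaluable (Section 6.8); 10% censoring allowance (Section 6.7).

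**1. The plan's boundaries.** The information fraction is 93/139 = 0.669. Linear spending gives 0.05 × 0.669 = 0.03345 at interim. With correlation √0.669 between the two statistics, the final nominal level that brings the total to 0.05 is 0.03246. These are the plan's 0.0335 and 0.0325.

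**2. The plan's operating characteristics.** Let k1 be the largest k with P(X ≤ k | n1, 0.195) < 0.0335, and k2 the largest k with P(X ≤ k | n2, 0.195) < 0.0325. Success has probability P(X1 ≤ k1) + P(X1 > k1, X1 + X2 ≤ k2), where X2 counts events among the n2 − n1 later subjects.

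- n1 = 93: P(X ≤ 10) = 0.0178 and P(X ≤ 11) = 0.0356, so k1 = 10.
- n2 = 139: P(X ≤ 18) = 0.0284 and P(X ≤ 19) = 0.0474, so k2 = 18.

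| Quantity | Table 2 | Exact |
|---|---|---|
| Interim success, 19.5% | 1.8% | 1.78% |
| Overall success, 19.5% | 3.8% | 3.65% |
| Interim success, 10.5% | 61.3% | 61.4% |
| Overall success, 10.5% | 87.1% | 86.9% |

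The table is reproduced apart from small differences in simulated figures.

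**3. Is there room at 93/139?** Keep k1 = 10 and raise the final limit to 19: the overall type I error becomes 5.31%. So 18 is already the largest limit allowed.

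**4. Other counts.** The exact rule keeps k1 and takes the largest final limit with overall type I error at or below 0.05.

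| n1/n2 | Final limit, plan vs exact | Type I error | Power at 10.5% |
|---|---|---|---|
| 93/140 | 18 vs 19 | 3.46% vs 4.99% | 86.4% vs 90.8% |
| 92/137 | 17 vs 18 | 3.07% vs 4.23% | 83.1% vs 88.1% |

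**5. Average over counts.** The documents give only a 10% allowance, so a distribution must be assumed: n1 ~ Bin(103, 0.90) and n2 − n1 ~ Bin(51, 0.90). The exact rule is then one event looser in 37.7% of realisations and never stricter. Mean power at 10.5% goes from 86.0% to 87.8%, and mean type I error from 3.8% to 4.3%. The gain is 2.9 points at a 12.5% event rate and 0.5 at 8.5%. At 10.5% it runs from 0.7 points (2% loss) to 2.3 (15% loss).

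**6. Validity of the plan's rule.** Over the evaluable counts enumerated, the largest overall type I error with the fixed cut-offs is 4.97%. The 5% limit holds away from 93/139 too, provided missingness is unrelated to outcome.

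**7. Whether fixing the number is the cause.** Rerunning the linear spending boundary at the actual information fraction gives no gain: mean power is 86.5% both ways on a flat grid of counts. The unused error comes from discreteness.

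**8. Stability of the exact rule.** Take 19 events in 140 evaluable, with no success at interim. The overall type I error of allowing 19 is 5.11% if n1 = 92, 4.99% if n1 = 93, and 5.78% if n1 = 94 (where k1 rises to 11). The same final data would fail, pass and fail. Under the plan the final limit depends on n2 alone and is 18 in all three cases.

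**9. Margin against outcome-related loss.** Suppose, for illustration, that 88% of subjects with events and 90.5% of those without are evaluable. At a true rate of 19.5%, the rate among evaluable subjects is 0.195 × 0.88 / (0.195 × 0.88 + 0.805 × 0.905) = 0.1906. Mean type I error is then 4.9% under the plan and 5.5% under the exact rule. With 10% lost overall, the mean reaches 5% at evaluability of 87.8% versus 90.5% under the plan (a gap of 2.7 points), and at 88.8% versus 90.3% under the exact rule (1.5 points).

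**The case for a change.** The strongest case for a change is that it needs no more patients and leaves the interim rule alone. The plan gives up power for the interim look, and averaged over plausible counts its power is 86.0%, not 87.1%. An exact rule recovers 1.8 points, about 5.2% of the trials that reach the final analysis (0.0177/0.3378), within the 5% the plan allows itself. It would have to be written in advance, since loosening a limit after seeing data is not credible. Nor does the plan say that the unused error is deliberate.

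The arithmetic stands. What does not follow is that the plan is wrong. The gain depends on an assumed distribution of counts and is nil at the planned ones. Part of the gap from 87.1% to 86.0% is simulation: exact power at 93/139 is 86.9%, so varying counts account for 0.9 points. The change is also not free. It uses up margin in a complete-case analysis where some loss is structural, because Section 5.2.2 follows subjects without an implant only to 30 days. A cautious variant that loosens only where the exact error is at most 0.045 gains just 0.6 points. Section 6.8 already states the 93 and 139 evaluable numbers beside the cut-offs, so a further note on where 87.1% applies would change no result.

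**Conclusion.** The concern does not hold. At 93 and 139 evaluable, the plan's rule already coincides with the exact 5% rule. At the other counts examined it stays valid, with type I error no higher than 4.97% when missingness is unrelated to outcome. The forgone power averages about 1.8 points at a 10.5% event rate, assuming independent 10% loss. Recovering it means accepting more type I error, less protection against outcome-related loss, and a success limit that can switch back and forth with one interim subject's evaluability. The plan discloses its error rate and power and accepts the cost of the interim look. Reasonable statisticians could choose either rule, and keeping 0.0325 is sound.

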**Table 2: Simulation results**

True Event Rate	Interim Analysis (IA) success	Overall study power with IA	Reject at IA but fail at Final	Study power without IA
19.5%	1.8%	3.8%	0.8%	4.9%
12.5%	37.9%	64.7%	2.1%	71.7%
11.5%	49.1%	77.0%	1.6%	82.8%

10.5%	61.3%	87.1%	1.0%	91.1%
9.5%	73.3%	93.7%	0.5%	95.9%
8.5%	83.5%	97.5%	0.2%	98.6%
7.5%	91.1%	99.3%	0.1%	99.6%
6.5%	96.0%	99.9%	<0.1%	99.9%

When data were simulated under the null hypothesis, i.e., the composite event rate is 19.5%, there is a risk of 1.8% that the null hypothesis will be rejected falsely at interim and an overall false positive risk of 3.8%, which is below the study-wise type I error rate of 0.05.

When data were simulated under the alternative hypothesis, e.g., if the true composite event rate is 10.5% as originally assumed in the sample size calculation, there is a 61.3% chance the study will meet its primary objective at interim with two thirds of the planned sample size and a risk of 1.0% of failing the final analysis after declaring success at interim. By adding the interim analysis, the overall power of the study decreases slightly to 87.1% from the original designed 90% power. However, if the true composite event rate is a few percentage points better than originally assumed, for example at 8.5%, there is a 83.5% chance the study will declare success at interim and the overall power of the study is 97.5% with very little risk of achieving success at interim but failing at final analysis.

The simulation results show that the proposed interim analysis can potentially achieve study success faster with two thirds of the planned sample size, particularly if the true composite event rate is lower than originally assumed. It is unlikely that a final analysis would fail after success is achieved at interim. The added interim analysis may cause some loss of overall study power, but the amount of loss is small.

## 7. CLINICAL EVENT REPORTING

The Principal Investigator (PI), or authorized designee, is responsible for the detection and documentation of events meeting the criteria and definitions set forth in Section 7.1. Collection of these events will begin immediately following subject enrollment (events occurring prior to becoming a treated subject as defined in 5.2.2 will be documented as medical history), during the index procedure through final subject follow-up visit or early termination.

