### 5.1.7. Diagnostic Angiogram

Prior to any study intervention, subjects meeting the clinical eligibility criteria for the study will undergo diagnostic angiography to better characterize the degree of atherosclerosis and ensure that the subject meets all angiographic inclusion and exclusion criteria.

Access should be gained per the institution's standard technique. The procedure begins at the time that arterial access is obtained.

All angiography shall be performed using the identical angles, magnification and angiographic technique as described in the "Angiography Guidelines" supplied by the Angiographic Core Lab. **It is important to use the specified calibrated measurement catheter so that the Angiographic Core Lab may properly assess the target lesion characteristics (e.g., reference vessel diameter, lesion diameter and length). Properly labeled angiographic-recorded media are to be uploaded or sent to the Angiographic Core Lab for evaluation.**

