### 5.2.1. Target Lesion(s) PTA

All subjects will undergo conventional PTA pre-dilatation at the target lesion site(s) previously identified by angiography. Prior to PTA, the Investigator shall identify (by visual estimation) the beginning and end of each target lesion(s). The target lesion(s) should have a combined (single or multiple lesions) **lesion length of less than or equal to 100 mm per side** (unilateral or bilateral disease). PTA shall be limited to predetermined treatment segment(s).

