#### Target Lesion including Dissection: Less than or equal to 100 mm

- If a flow-limiting dissection occurs, and extends beyond the target lesion(s), but the total length of the target lesion(s) plus the dissected segment is less than or equal to 100 mm in length, the LIFESTREAM™ Covered Stent(s) may be used to properly treat the dissected segment.

Target Lesion including Dissection: Greater than 100 mm

- If the total length of the target lesion(s) plus the dissected segment extends greater than 100 mm, the Investigator should **not** place the LIFESTREAM™ Covered Stent(s) to treat the dissected segment. The Investigator should use standard of care practices to treat the dissected segment. As the study device will **not** be introduced, these subjects requiring treatment of dissected segments extending greater than 100 mm will be treated as an intra-procedure screen failure and will not be included in the ITT analysis.

Dissection including the internal iliac (hypogastric) artery or other important collaterals

- If a dissection occurs at the origin of the hypogastric artery (or other important collateral), the Investigator should **not** place the LIFESTREAM™ Covered Stent(s) to treat the dissected segment. The Investigator should use standard of care practices to treat the dissected segment, which may include placing an approved iliac bare metal stent in order to treat the dissection without occluding the hypogastric (or collateral) artery. As the study device will **not** be introduced, these subjects will be treated as an intra-procedure screen failure and will not be included in the ITT analysis. However, if the hypogastric (or collateral) artery is already occluded and the lesion (including dissection) is less than or equal to 100 mm in length, the LIFESTREAM™ Covered Stent(s) may be used to properly treat the dissected segment as long as the device is above the inguinal ligament.

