### Treated Subject

After the subject has met all eligibility criteria, undergone successful PTA of the target lesion(s), and the LIFESTREAM™ Covered Stent catheter is introduced (i.e., delivery system enters the subject's body), the subject will be considered to be a treated subject in the study. Treated subjects will continue study participation through the study's 36-month follow-up period. Subjects that do not receive the LIFESTREAM™ Covered Stent implant (but the LIFESTREAM™ Covered Stent catheter was introduced) will be followed through the 30-day follow-up visit to assess any safety events and will be included in the ITT and PP analyses (see Section 6).

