### 5.2.6. Guide Catheter/Sheath Removal Guidelines

Immediately following the procedure, in accordance with the institution's standard of care practices, heparin should be discontinued. An on-label vascular closure device may be used at the discretion of the Investigator, in accordance with the manufacturer's directions. The index procedure ends at the time that the last guidewire is removed.

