### 7.3. Relationship of Adverse Event to Device(s)/Procedure

Investigators will assess each AE/SAE for its relationship to the study device (LIFESTREAM™ Covered Stent) or procedure as follows.

1) Assess each AE for its relationship to the device or procedure as follows:

- **Device(s) Related:** This category should be restricted to AEs directly attributable to the study device(s) used as part of the index procedure.
- **Procedure Related:** A procedure includes any activity performed during the index procedure.

2) The following categories should be used for assigning the certainty of the relatedness:

- **Definitely Related:** An AE is definitely related if it is obvious, certain or there is little doubt regarding the relationship.
- **Possibly Related:** An AE is possibly related if it is capable of being related but relatively unlikely or there insufficient information to determine if the AE is related to the device or procedure.
- **Not Related:** An AE is not related if it is determined that there is no plausible association.

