**APPENDIX 1: Time and Events Schedule**

Observation	Baseline/ Screening	Index Procedure	Hospital Discharge 	30 d  (± 7d)	6 mo  (± 30d)	9 mo (± 30d)	12, 24, & 36 mo (± 30d)
Eligibility Criteria	✓	✓					
Informed Consent	✓						
Demographics	✓						
Medical History	✓						
Pregnancy test	✓ 						
Labs (BUN or Creatinine, CBC including Platelets)	✓						
Concomitant Medications	✓	✓	✓	✓	✓	✓	✓
Comprehensive Physical Exam	✓		✓	✓		✓	✓
Angiogram	✓ 	✓ 					
Resting ABI	✓			✓		✓	✓
Rutherford (Category & Grade)	✓			✓		✓	✓
Adverse Event Assessment		✓	✓	✓	✓	✓	✓
TLR/TVR Assessment				✓ 	✓ 	✓ 	✓ 
Color Flow Duplex Ultrasound				✓ 		✓ 	✓ 
WIQ	✓ 			✓		✓	✓

Subjects meeting the criteria for deployment failure will be evaluated at hospital discharge and the 30-day follow-up visit to assess and document any AEs or SAEs that may have occurred since the index procedure.

Telephone Screen

Perform pregnancy test (urine or blood) for women who are of childbearing potential ≤ 14 days prior to the index procedure.

Send images to Angiographic Core Laboratory

Send images to Ultrasound Core Laboratory

Complete WIQ ≤ 30 days prior to the index procedure

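### Section 7 files events before study-catheter introduction as medical history, so complications of the mandatory pre-dilatation can drop out of the AE/SAE data of treated subjects

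*Combined protocol and SAP*

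**What the plan says.** Section 7 gives the collection window in one sentence. Collection starts right after enrollment, which Section 5.2.2 places at consent, and runs through the index procedure to the last follow-up. A parenthesis in that sentence adds that "events occurring prior to becoming a treated subject as defined in 5.2.2 will be documented as medical history".

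Section 5.2.2 makes a subject treated only when three things have happened: eligibility is met, PTA of the target lesion has succeeded, and the study delivery system has entered the body.

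The steps before that point are described as follows:

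- Section 5.1.7, on the diagnostic angiogram: "The procedure begins at the time that arterial access is obtained".
- Section 5.2.1, under the heading Index Procedure: "All subjects will undergo conventional PTA pre-dilatation at the target lesion site(s) previously identified by angiography".
- Section 5.2.6: "The index procedure ends at the time that the last guidewire is removed".

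Two further places bear on what counts as a procedural event. Section 7.3 says of relatedness: "A procedure includes any activity performed during the index procedure". The row "Adverse Event Assessment" in Appendix 1 is ticked in the Index Procedure column, with no footnote restricting it to part of the procedure.

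**The concern.** The dividing line in the parenthesis falls in the middle of the index procedure. Balloon pre-dilatation is required of every subject and can injure the vessel. Section 5.2.1 foresees dissection after PTA, and Section 9 lists vessel perforation, dissection and rupture among the potential adverse effects. An investigator who follows the parenthesis would enter such an injury as history that the subject brought to the study, although a study-mandated step caused it.

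At stake is the completeness of procedure-related AE and SAE reporting in the ITT population. An event filed as history may not be graded for seriousness and relatedness, and may not go to the sponsor within one business day. Sites could also read the sentence differently and so report unlike data. The trial has one arm, so no concurrent control shares the omission, and any loss makes the device look safer.

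**Working it through.** No arithmetic decides this point. The check is to place the events of the index procedure in order and ask what each rule makes of them.

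1. **Arterial access, angiogram, crossing.** Section 5.1.7 starts the procedure at arterial access. The subject is not yet treated. The parenthesis makes an event here medical history. That this phase belongs to the index procedure is an inference: Section 5.1.7 sits under screening and baseline, does not use the word index, and Appendix 1 ticks the angiogram in both the Baseline/Screening and the Index Procedure columns.
2. **Pre-dilatation.** It lies in Section 5.2, so it is plainly inside the index procedure. The subject is still not treated, because Section 5.2.2 requires PTA to have succeeded first. The parenthesis again gives medical history. The main clause of Section 7, Section 7.3 and the Appendix 1 tick all point to a procedure-related AE.
3. **Study catheter enters the body.** Treated status begins. From here to removal of the last guidewire (Section 5.2.6), all the rules agree.

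The disagreement is therefore certain for step 2 and probable for step 1.

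**Does the affected phase concern analysed subjects?** Yes. Under Section 5.2.1, a flow-limiting dissection that extends beyond the target lesion may be covered with the study stent if lesion plus dissection is no longer than 100 mm. That subject becomes treated and enters the ITT population (Section 6.1). The dissection itself arose before treated status.

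**Is the event recovered later?** Not clearly. The discharge assessment in Section 5.3 asks for events since the index procedure, which need not include events during its early part.

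**Does it reach an endpoint?** Taking the components in turn:

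- TLR, as defined in Section 3.1, follows the index procedure, and restenosis is read on follow-up duplex. Neither arises in this phase.
- A subject who dies before catheter introduction is not in the ITT population. A later death occurs after treated status and must be reported whatever its cause (Section 7.4.1).
- This leaves, in the main, an MI between access and catheter introduction in a subject who is then treated. Section 3.1 assigns MI to the CEC without mentioning the Section 7 cut-off.
- Dissection is a component of neither the primary endpoint nor Acute Procedure Success. Section 3.2 also states no start point tied to treated status for the peri-procedural complications.

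**The case against.** **The parenthesis may be a deliberate carve-out.** A specific exception can sit inside a general clause. Collection during the index procedure would then mean from catheter introduction to last guidewire removal. This stands as a possible reading, so a reader should not infer that Section 7 is flatly self-contradictory or impossible to follow. It does not remove the problem, because on this reading the exclusion of pre-dilatation complications is intended. The other benign reading is that the parenthesis was meant for the time between consent and the start of the procedure. The text does not say so; it refers to treated status and not to arterial access.

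**Few of the cited sections state a rival rule.** This is correct. Sections 5.1.7, 5.2.1, 5.2.2 and 5.2.6 only fix boundaries. Section 7.3 classifies relatedness and does not set a collection window, and the Appendix 1 tick gives no start point. The tension is mainly within Section 7, with these two as support.

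**Other rules catch such events.** In part they do. Sections 7.4 and 14 require prompt reports of procedure-related AEs and SAEs, with no treated-subject qualifier. Deaths (Section 7.4.1) and emergency interventions (Section 11.5) have their own notice rules. Section 7.5.3 has the CEC review all complications, and the sponsor forwards source reports on request. However, that section gives the CEC the eCRFs of reported AEs and names no routine source for a complication entered as history.

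**A stronger inference is tempting:** that the primary endpoint is biased, or its false-positive rate raised. The documents do not support it. Nothing ties CEC adjudication to the Section 7 cut-off, the CEC charter is not among the documents, and no rate of events in this phase is given. Any error-rate figure would rest on an invented input.

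**Conclusion.** The point holds as a defect in safety recording. As worded, Section 7 takes complications of the mandatory pre-dilatation out of AE/SAE collection in subjects who go on to be treated and analysed. By inference it does the same for complications of access and crossing. Procedure-related AEs and SAEs may be under-recorded, and sites may report inconsistently, in a direction that favours the device.

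The size cannot be stated, and the number of affected subjects may be zero. The conclusion assumes that at least some sites follow the parenthesis literally; sites that give priority to Sections 7.3 and 7.4 would lose nothing. No effect on the primary endpoint or on Acute Procedure Success is shown. One would arise only if adjudication adopted the same cut-off or if relevant events never reached the CEC. The change should be made because the rule is explicit and easily corrected, not because the primary result is in doubt.

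**What to change.** In Section 7, limit medical history to events before arterial access at the index procedure. State that, for every subject who becomes treated, AE/SAE collection and CEC review of procedure-related events run from that arterial access. Put the same start point in the eCRF instructions and the CEC charter, and word the discharge assessment in Section 5.3 so that it covers events during the procedure as well as after it.

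The cost is one sentence in the protocol and matching lines in those other places. Sites must note events from access onward and enter them as AEs once the subject becomes treated. A few more AEs will be reported, and the safety figures may look slightly less favourable. Treatment, sample size, analysis populations and the primary test do not change.
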